1.2 Intercurrent events

The tables below cover all planned efficacy analyses, except for sensitivity analyses.

The strategies/approaches for handling ICEs will be as follows:

- *Treatment Policy*: all data will be included in the analysis, regardless of whether the participant remains on the assigned investigational treatment or discontinued. This will reflect the treatment effect regardless of the ICE.
- *Hypothetical*: data will be modified to mirror its value had an ICE not happened (under some hypothetical conditions). One such hypothetical condition is that the ICE occurred completely at random. In this case, all post-ICE data are set to missing (removed) and imputed under the assumption of missing at random (MAR). This strategy can be applied to ICEs which are considered uninformative with respect to the effect of interest. As a default approach, this strategy will be applied to any occurrence of an ICE affecting the existence of measurements and maximum likelihood (ML) imputation will be used for continuous gaussian-distributed endpoints where a linear mixed effect model is used for analysis (Schafer and Graham, 2002). Alternative imputation approaches will also be considered for ICEs which are considered informative with respect to the effect of interest, under the assumption of missing not at random (MNAR), such as reference-based imputation (RBI) approaches (Carpenter, Roger & Kenward, 2013) for continuous endpoints and non-response imputation (NRI) where missing responder status is imputed as non-response for binary endpoints (Floden and Bell, 2019), as well as causal inference methods (Lasch et al., 2022). This approach will reflect the treatment effect had the ICE not occurred.
- *Composite*: ICE data will be incorporated into the endpoint being analyzed. This approach will be used for the MDS-UPDRS Part II/III time to worsening analyses; a composite endpoint of time to worsening or time to ST initiation will be used as ST initiation is considered representative of a negative outcome.

Table 1-2: Overview of handling strategies for ICEs, ICE-like protocol deviations and study termination or loss to follow-up for MDS-UPDRS estimands

		MDS-UPDRS Part I-III sum score and Part I/II/III subscales	
Estimand	Primary, key secondary and secondary	Key secondary	Secondary and supplementary
Handling ICE (ST initiation)	In the absence of ST initiation	ST initiation as part of the response	Regardless of ST initiation
Population summary measure	For Part I-III sum score: Difference in slope of progression at 12 months (primary) and difference in mean at 12	For Part III subscale: Difference in RMET (time to confirmed first 5-point increase or ST	For Part I-III sum score: Difference in mean at 12 and 18 months (supplementary)

Table 1–2: Overview of handling strategies for ICEs, ICE-like protocol deviations and study termination or loss to follow-up for MDS-UPDRS estimands

	
and 18 months (key secondary and supplementary)^a
 
For Part III subscale: Difference in slope of progression at 12 months (key secondary)
 
For Part III subscale and Part III ePD subscore^a: Difference in mean at 12 and 18 months (key secondary)
 
For Part I/II subscale: Difference in mean at 12 and 18 months (secondary)
	
initiation) within 18 months (key secondary)
 
For Part II subscale: Difference in RMET (time to confirmed first 3-point increase or ST initiation) within 18 months (supplementary)
	
For Part I/II/III subscales: Difference in mean at 12 and 18 months (supplementary)

ICE & ICE-like protocol deviations			
ST initiation (Non-MAO-B Inhibitors) ^c	Hypothetical (set to missing & impute all post ICE visit data – MAR/ML)	Composite (ICE is part of the endpoint)	Treatment policy (Include post-ICE data)
ST initiation (MAO-B Inhibitor) ^c	Hypothetical (set to missing & impute all post ICE visit data – MAR/ML)	Composite (ICE is part of the endpoint)	Treatment policy (Include post-ICE data)
Treatment discontinuation (Lack of efficacy or AE)	Treatment policy (Include post-ICE data)	id	id
Treatment discontinuation (Other causes)	Treatment policy (Include post-ICE data)	id	id
Important ICE-like protocol deviations			
with long-term impact ^d	Hypothetical (set to missing & impute all post ICE visit data – MAR/ML)	Hypothetical (set to missing & treat as right-censored (non-event) at time of initial IPD)	id
With short-term impact ^d	Hypothetical (set to missing & impute single post-ICE visit data – MAR/ML)	Hypothetical (ignore)	id

Table 1–2: Overview of handling strategies for ICEs, ICE-like protocol deviations and study termination or loss to follow-up for MDS-UPDRS estimands

Death or serious injury (all causes)	Actual missing: impute all post ICE visit data – MAR/ML	Actual missing: treat as right-censored (non-event) at time of termination	id
COVID-19-related ICEs without Treatment discontinuation or Study termination	Treatment policy (Include post-ICE data)	id	id
Missed visits, study termination and loss to follow-up			
Missed visit(s) (intermittent) ^f	Actual missing: impute visit data – MAR/ML	Actual missing: ignore	Actual missing: impute visit data – MAR/ML
Study termination: Treatment-related	Actual missing: impute all post termination visit data – MAR/ML ^g	Actual missing: Imputed as non-response (event) to randomised treatment under MNAR ^e	Actual missing: impute all post termination visit data – MAR/ML
Study termination and loss to follow-up Other/unknown causes	Actual missing: impute all post termination visit data – MAR/ML	Actual missing: will be treated as right-censored (non-event) at the time of termination	Actual missing: impute all post termination visit data – MAR/ML

AE=Adverse Event; COVID-19 = Coronavirus Disease 2019; ICE=Intercurrent Event; id = idem, “the same” across rows; MAR = Missing at Random; ML = Maximum Likelihood; MDS-UPDRS=Movement Disorder Society-Unified Parkinson’s Disease Rating Scale; RMET=Restricted Mean Event Time; ST = Symptomatic Treatment.

^a For the estimands of MDS-UPDRS Part I–III sum score, Part III subscale and Part III ePD subscore, de-mediated difference in mean at Month12/18, the handling strategies outlined in this table for ST initiation and for study termination do not apply. Details on the handling strategies to be applied for ST initiation and study termination will be provided in [Appendix 5](#).

^cSee [Section 5.3.3.3](#) for how to determine which type of ST a medication is.

^dThe category that each protocol deviation falls into will be defined outside of the SAP, in the protocol deviation specifications or a separate document. Only important protocol deviations can be ICEs, but not all important protocol deviations will be defined as ICEs.

^eTreatment-related study-termination is classed as an event in the RMET analysis for MDS-UPDRS Part III.

^fThis does not apply to missing baseline data. Baseline data will not be imputed.

^gST de-mediation approaches may implement alternative imputation strategies.

Note: In case of an event preventing a participant from attending a particular scheduled clinic visit with a MDS-UPDRS assessment (for example, due to COVID-19), this will be considered a minor protocol deviation and MDS-UPDRS data collected for this participant in clinic at future visits will be included in the analyses. Any imputation of the missing visit data will apply a MAR assumption.

Note: When MDS-UPDRS is collected at home rather than in clinic not all MDS-UPDRS data will be collected (rigidity assessments will be missing) and the Part III and total scores cannot be calculated. Any imputation of the missing visit data will apply a MAR assumption.

Note: Where missing data is to be imputed under a MAR assumption, whether in the case of either intermittent missing or of longitudinal missing (study termination or loss to follow-up), a ML approach will be used for all LMEM-based modelling.

Note: the Part II emerging symptoms estimand is not covered in this table. The ICE handling strategies for this estimand are covered in [Section 5.3.2.1.7](#).

Table 1–3: Overview of handling strategies for ICEs, ICE-like protocol deviations and study termination or loss to follow-up for other estimands

	DaT-SPECT mean Striatum SBR	ST intake	MoCA
Estimand	Secondary	Secondary, other secondary and supplementary	Other secondary
Handling ICE (ST initiation)	Regardless of ST initiation	ST initiation/intake as the response	Regardless of ST initiation
Population summary measure	Difference in mean change from Baseline at 12 months and 18 months (secondary)	Difference in RMET (time to ST initiation) within 18 months (secondary), Odds ratio of ST intake at 12 months (other secondary) and 18 months (secondary), Relative Risk of ST intake at 12 and 18 months (sensitivity), Hazard ratio of ST intake at 18 months (supplementary)	Difference in mean at 18 months (other secondary)
ICE & ICE-like protocol deviations			
ST initiation (MAO-B Inhibitors) ^b	Hypothetical (set to missing & impute all post ICE visit data – MAR/ML)	NA	Treatment policy (Include post-ICE data)
ST initiation (Non-MAO-B Inhibitors) ^b	Treatment policy (Include post-ICE data)	NA	Treatment policy (Include post-ICE data)
Treatment discontinuation (Lack of efficacy or AE)	Treatment policy (Include post-ICE data)	id	id
Treatment discontinuation (Other causes)	Treatment policy (Include post-ICE data)	id	id
Change in scanner	Treatment policy (Include post-ICE data)	NA	NA
Important ICE-like protocol deviations			

Table 1–3: Overview of handling strategies for ICEs, ICE-like protocol deviations and study termination or loss to follow-up for other estimands

With long-term impact ^c	Hypothetical (set to missing & impute all post ICE visit data – MAR/ML)	Hypothetical (set to missing & treat as right-censored (non-event) at time of initial IPD)	id
With short-term impact ^c	Hypothetical (set to missing & impute single post-ICE visit data – MAR/ML)	Hypothetical (ignore)	Treatment policy (Include post-ICE data)
Death or serious injury (all causes)	Hypothetical (set to missing & impute all post ICE visit data – MAR/ML)	Actual missing: treat as right-censored (non-event) at time of termination	id
COVID-19 related ICEs without Treatment discontinuation or study termination	Treatment policy (Include post-ICE data)	id	id
Missed visits, study termination and loss to follow-up			
Missed visit(s) (intermittent) ^e	Actual missing: impute visit data – MAR/ML	Actual missing: ignore	Actual missing: impute visit data – MAR/ML
Study termination: Treatment-related	Actual missing: impute all post termination visit data – MAR/ML	Actual missing: Imputed as non-response (event) to randomized treatment under MNAR ^d	Actual missing: impute all post termination visit data – MAR/ML
Study termination and loss to follow-up: Other/unknown cause	Actual missing: impute all post termination visit data – MAR/ML	Actual missing: will be treated as right-censored (non-event) at the time of termination	Actual missing: impute all post termination visit data – MAR/ML

AE=Adverse Event; COVID-19 = Coronavirus Disease-2019; DaT-SPECT=Dopamine Transporter Imaging with Single Photon Emission Computerized Tomography; ICE=Intercurrent Event; id = idem, “the same” across rows; MAR = Missing at Random; ML = Maximum Likelihood; MNAR = Missing Not at Random; MoCA=Montreal Cognitive Assessment; RMET=Restricted Mean Event Time; SBR=Specific Binding Ratio; ST=Symptomatic Treatment.

^bSee [Section 5.3.3.3](#) for how to determine which type of ST a medication is.

^cThe category that each protocol deviation falls into will be defined outside of the SAP, in the protocol deviation specifications or a separate document. Only important protocol deviations can be ICEs, but not all important protocol deviations will be defined as ICEs.

^dTreatment-related study-termination is classed as an event (ie, non-response) in the RMET analysis for ST initiation.

^eThis does not apply to missing baseline data. Baseline data will not be imputed.

Note: Where missing data will be imputed under a MAR assumption, whether in the case of either intermittent missing or longitudinal missing (study termination or loss to follow-up), a ML approach will be used for all LMEM-based modelling.

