#### ICEs and handling strategies

The main ICEs will be study termination and lost to follow up: both will be handled using a ‘hypothetical’ strategy where the post-ICE data will be set to missing.

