1.2.6 Study termination and loss to follow-up

A participant may withdraw from the study at any time at his/her own request or may be withdrawn at any time at the discretion of the Investigator for safety, behavioral, IMP compliance, or administrative reasons. If a study participant withdraws or is withdrawn, he or she should be encouraged to perform the End-of-Treatment (EOT) Visit and the Safety Follow up Visit approximately 30 days after last dose of IMP.

Study termination will only be considered treatment-related if the reason for termination is 'lack of efficacy'. As a default approach, MAR will be assumed and the implicit imputation of likelihood-based linear models (for gaussian distributed outcomes), will be applied to any occurrence of study termination (including treatment-related termination) and the event will be ignored. For event-based outcomes, the approach will depend on whether the termination is considered to be treatment-related or not. For treatment-related termination, imputation assuming non-response to treatment will be applied (for example, for time to ST initiation we would impute treatment-related termination as a progression-related 'event'). For other causes of study termination (including loss to follow-up) data will be considered right censored at the time of termination (and ignored).

In well-designed clinical studies it is reasonable to assume that dropout patterns follow the MAR mechanism, although missing not at random (MNAR) data cannot be ruled out (Liu-Seifert, 2015). As an alternative approach, a different hypothetical strategy, such as a reference-based imputation (RBI) approach (for gaussian distributed outcomes) will be used when participants terminate the study for treatment-related reasons for MDS-UPDRS-based continuous endpoints estimands (Appendix 5).

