5.3.2.4.2 Intake of ST

Definitions of endpoints

ST intake will be analyzed at both 12 and 18 months. For both estimands, the participant level endpoint is a binary variable indicating whether the participant has started ST or not, at 12 and 18 months respectively.

Main analytical approach

Full details on the ICE handling for these estimands can be found in [Section 1.2](#). The main ICES for these estimands will be study termination and loss to follow up (see details in [Table 1-3](#)).

At both time points, the population-level summary will be the population odds ratio of ST intake between:

- UCB0599 high dose (360mg/day) and placebo
- UCB0599 low dose (180mg/day) and placebo

In other words, population ratio of odds of ST intake in the presence of UCB0599 over odds of ST intake in the absence of UCB0599.

For both analyses a logistic regression will be performed, with gender and age at Baseline included as covariates. Summary tables will be produced displaying the odds ratios, 95% confidence intervals for the odds ratios, and the p-values for each comparison. This summary will also include the number of participants in each treatment group who are/are not on ST at the timepoint being analyzed.

Sensitivity analyses

A relative risk (RR) regression using a log-link binomial generalized linear model (GLM) will also be fitted to this binary outcome to obtain the RR point estimates and corresponding 95% CIs. This regression will use the same covariates and fixed effects as the logistic regression model. This analysis will be conducted for 12 and 18 months.

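### SAP Table 1-3 gives other-cause dropouts a censored, non-event label that also governs the symptomatic-treatment odds ratio and relative risk, whose models cannot use a censoring time

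*SAP*

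**What the plan says.** SAP Table 1-3 has a single ST-intake column. Its summary-measure row lists RMET, the hazard ratio, and also "Odds ratio of ST intake at 12 months (other secondary) and 18 months (secondary") and "Relative Risk of ST intake at 12 and 18 months (sensitivity").

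For study termination from other or unknown causes and for loss to follow-up, that column says "Actual missing: will be treated as right-censored (non-event) at the time of termination". The rows for death or serious injury and for important deviations with long-term impact use the same non-event label. The row for treatment-related termination goes the other way: "Actual missing: Imputed as non-response (event) to randomized treatment under MNAR". Its footnote d refers only to the RMET analysis.

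SAP 1.2.6 defines the split: "Study termination will only be considered treatment-related if the reason for termination is 'lack of efficacy". Withdrawals from the study for adverse events therefore fall in the other-cause row. For event-based outcomes the same section says that, for other causes, "data will be considered right censored at the time of termination (and ignored").

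SAP 5.3.2.4.2 defines ST intake as a binary variable at Months 12 and 18. It says "The main ICES for these estimands will be study termination and loss to follow up", refers to Table 1-3 for details, and then fits a logistic regression (OR) and a log-link binomial model (RR) with gender and age as covariates. No censoring weights are mentioned.

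Protocol 9.3.3.2 and 9.3.3.3 use a hypothetical strategy for these events, "where the post-ICE data will be set to missing". SAP Appendix 2, which lists changes to protocol-planned analyses, does not mention the point.

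**The concern.** Right-censoring is a sound instruction for RMET or Cox regression, where a participant contributes time at risk up to departure. A binary model needs a yes or a no at the fixed month. The only part of the cell a programmer can carry into it is the non-event label, meaning not on ST. Every other-cause leaver without earlier ST would then lower the ST rate of their arm.

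If such dropout differs between arms, the OR and RR move away from 1 with no effect on the need for ST. The SAP accepts that it may differ. Section 3.4 says more participants could be lost on active because of adverse events, or fewer because of efficacy. Section 5.3.2.4.1 says termination may be higher or lower on active and adds arm-specific censoring weights for time to ST. The OR and RR come from the same participants and the same ST starts but receive no such protection.

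**Working it through.** **The plan's own figure.** Neither document gives a power or event rate for the ST-intake OR or RR. The one reproducible design figure is the primary sample size. From SAP Table 3-1, σ² = 154.0 + 31.1 = 185.1, 1 − ρ = 31.1/185.1 = 0.168, r × N₁Var(T) = (0.43/185.1) × 85.57 = 0.199, and Δ² = 0.27²/185.1 = 0.000394. With the allocation factor of 2 applied to the whole bracket, n = 2 × (0.168 + 0.199) × 2.56² / (85.57 × 0.000394) = 142.66 from unrounded inputs, or 143 per arm. Z = 2.56 matches a one-sided 10% test with 90% power. I use 450/3 = 150 per arm and a one-sided 10% test below.

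**Inputs.** SAP 3.2 gives ST initiation by Month 12 as 20% (planning) and 58% (PPMI). It gives non-ST loss by Month 12 as 5% + 10% = 15%, and a further 10 points each of ST initiation and dropout by Month 18, so 30% on ST and 25% dropout. The 60% ST rate at Month 18 is my assumption. The steps of 5, 10 and 15 points more dropout on active follow the three 5% components in SAP 3.4, which were written for DaT-SPECT.

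**Formula.** Take no true effect, with exponential and independent times to ST and to dropout. With p the ST probability and d the dropout probability by the time point, a = −ln(1 − p) and b = −ln(1 − d). The share observed to start ST before leaving is

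q = a/(a + b) × [1 − (1 − p)(1 − d)].

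All other leavers are coded as not on ST.

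**Worked case (Month 12, p = 0.20, dropout 15% placebo and 25% active).** Placebo: a = 0.2231, b = 0.1625, q = 0.5786 × 0.32 = 0.185. Active: b = 0.2877, q = 0.4368 × 0.40 = 0.175. OR = (0.1747/0.8253)/(0.1852/0.8148) = 0.93.

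**All settings, active dropout +5 / +10 / +15 points, true OR and RR = 1:**

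| Setting | Placebo dropout | OR | RR | One-sided 10% rejection |
|---|---|---|---|---|
| Month 12, 20% on ST | 15% | 0.97 / 0.93 / 0.90 | 0.97 / 0.94 / 0.92 | 12% / 15% / 18% |
| Month 12, 58% on ST | 15% | 0.95 / 0.90 / 0.85 | 0.98 / 0.95 / 0.92 | 15% / 21% / 29% |
| Month 18, 30% on ST | 25% | 0.96 / 0.92 / 0.88 | 0.97 / 0.94 / 0.91 | 13% / 17% / 21% |
| Month 18, 60% on ST | 25% | 0.94 / 0.89 / 0.84 | 0.97 / 0.95 / 0.92 | 15% / 22% / 31% |

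With equal dropout the OR is 1.00 and rejection is 10%. Swapping the arms inverts the OR: 10 points less dropout on active gives 1/0.93 = 1.07 in the worked case.

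**Lack-of-efficacy terminations as events.** If a share of the leavers without ST, equal in both arms, is coded as events, the +10-point OR changes as follows:
- Month 12, 20% on ST: 0.93 at a 0% share, 0.99 at 10%, 1.07 at 25%.
- Month 18, 30% on ST: 0.92, 0.96, 1.02.
- Month 18, 60% on ST: 0.89, 0.91, 0.95, and 1.02 only at a 50% share.

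**Excluding leavers without ST.** If leavers without ST are dropped and those who started ST first are kept, the odds in each arm are q/[(1 − p)(1 − d)]. In the worked case the OR is (0.1747/0.60)/(0.1852/0.68) = 1.07. Across settings it is 1.07 to 1.09 at +10 points and 1.11 to 1.15 at +15.

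**Arm-specific Kaplan-Meier risk at the time point** (the covariate-free counterpart of arm-specific censoring weights). In 4,000 simulated trials for each of 16 scenarios, the OR was 0.99 to 1.01 and one-sided 10% rejection was 9.3% to 10.5%.

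**The case against.** The best reply is that non-event coding in the logistic model is not settled. The cell begins by calling the data missing, SAP 1.2.6 adds that they are ignored, footnote d speaks only of RMET, and SAP section 1 follows the protocol unless the SAP specifies otherwise. This stands in part: the firm defect is an unreconciled rule that a binary model cannot apply as written. It does not clear the plan. Table 1-3 does specify a rule and names the OR and RR. The SAP's Amendment 3 change log says detail was added to these rows for time-to-event and binary endpoints. Reading ignored as excluding leavers without ST gives bias in the opposite direction.

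A second reply is that adverse events first lead to stopping study medication, not to missing ST status. Table 1-3 handles treatment discontinuation by treatment policy, and Protocol 7.2 separates stopping medication from leaving the study. That is fair and limits the expected imbalance. However, Protocol 6.8 and SAP 5.1.2.1.3 send participants who stop early to the End of Treatment and Safety Follow-up visits, so some loss of later ST status is plausible.

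Third, these are secondary and sensitivity analyses in a study the SAP calls exploratory, with no multiplicity control. RMET with arm-specific weights and Cox regression address the same question without coding censored participants as non-users. This stands, and it limits the consequence.

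A reader might infer that every dropout is coded as not on ST, so that the analysis leans towards active drug. The documents do not support that. Lack-of-efficacy terminations are imputed as events in the same column, the SAP allows imbalance in either direction, and equal dropout gives no bias.

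**Conclusion.** The concern holds as a conflict between Table 1-3, SAP 1.2.6 and the protocol over how other-cause leavers enter the ST-intake OR and RR. The literal table reading is biased whenever such dropout differs between arms. With no true effect and more dropout on active, the OR is about 0.94 to 0.97 at +5 points, 0.89 to 0.93 at +10 and 0.84 to 0.90 at +15. The one-sided 10% error rate rises to 12% to 15%, 15% to 22% and 18% to 31% respectively.

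These figures assume independent exponential times, 20% to 58% on ST at Month 12, 30% to 60% at Month 18, placebo dropout of 15% and 25%, and no lack-of-efficacy terminations. The size of any imbalance is an assumption. More extreme values can be produced: 70% on ST at Month 18 with 25% against 40% dropout gives an OR of 0.81. Neither document gives such rates, so values of that size should not be taken as expected. The direction reverses if active has less dropout. RMET and Cox are not affected in this way.

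**What to change.** - Limit the censored, non-event wording in the ST-intake column of Table 1-3 to RMET and Cox.
- For the Month 12 and Month 18 OR and RR, keep ST starts observed before termination as events and treat ST status after other-cause termination, loss to follow-up, death or serious injury, or a long-term important deviation as missing. Then use arm-specific inverse-probability-of-censoring weights or multiple imputation of ST status.
- Do not simply exclude leavers without ST. Keep non-event coding, if wanted, as a labelled sensitivity analysis.
- State whether lack-of-efficacy terminations count as events in the OR and RR, and align footnote d.
- Reconcile SAP 1.2.6 with the table and record any remaining departure from Protocol 9.3.3.2 and 9.3.3.3 in Appendix 2.

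The cost is a SAP text change made before unblinding and some programming. The arm-specific censoring weights are already planned for RMET. No data collection changes.
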